 in the study but after non-compliance and at least 3 documented, attempted contacts
 appropriately spaced 1-5 days apart, the family member will be considered LTF. Patients and
 family members who reach this status have no additional follow-ups or study requirements.
 Patients and family members who are assigned this status must be maintained on the
 enrollment log.
 - A family member who returns the study team's contacts within 1 week of last attempted contact may resume study participation.
 - A family member who has completed at least T1, T2, and T3 will be included in the overall target enrollment, even if deemed LTF for T4.
- Completed: defined as any family member who both consented and randomized to the study and completed T1-T4 (or at least 75% of the surveys). Family members and patients who reach this status have no additional follow-up or study requirements. Family members and patients who are assigned this status must be maintained on the enrollment log.

Protocol Version: 5.1 Dated: 13 June 2022 Page 13 of 42

Study data collection

Each consented family member will be asked to complete four surveys, as well as up to two meetings (for intervention group participants). Appendix 4 shows the timeline and acceptable time frames within which survey responses are allowed. Note that some latitude is provided given the possibility for weekends, etc.

- Baseline, Survey 1 (Day 1; up to 3 days allowed post-consent): this will occur generally on the day of consent. At this time, the following will occur:
 - App Registration
 - Survey 1 (T1) Completion
 - Randomization (if eligible)
- ICU Family Meeting for intervention group: The ICU attending will initiate a one-on-one family meeting to discuss the reported family needs. This is to occur prior to the completion of Survey 2 (T2).
- Survey 2: (Day 4; up to 4 days allowed post-randomization)
- Need-focused Palliative Care Family Meeting for intervention group: As noted above, this meeting will be triggered by a family member's T2 NEST score that is either ≥25 or higher than their T1 NEST score. The ICU attending and the Palliative Care team will meet with the family member together if at all possible to discuss the reported family needs. This meeting is to occur prior to the completion of Survey 3 (T3).
- Survey 3: (Day 8 up to 4 days allowed)
- Survey 4: (Day 90; up to 28 days allowed)

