Transcribed interviews will be analyzed using a content analysis technique that combines *structural* (e.g., intervention component, palliative care process barriers) and *magnitude coding* (e.g., theme intensity) with *inductive coding* (e.g., variations in outcomes not captured by instruments).⁴⁰ The study team will separately code 10 interviews, discuss the generated codes, and create an initial code book by consensus. The code book will then be used by the study team for the next 10 transcribed interviews (with the PI coding each 5th interview). The final code book will be organized into categories used to generate themes of mechanistic and process elements. Narrative case summaries will be constructed and matrixed by patient case using *qualitative* analytic themes and *quantitative* data (e.g., triggers, needs, psychological distress, app use analytics). Across-case comparisons will be made using meta-matrices to search for patterns in intervention mechanisms of action common across theoretically- and empirically-derived categories of cases.⁴¹ Next, *process tracing* will be used to

Protocol Version: 5.1 Dated: 13 June 2022 Page **15** of **42**

explore how particular outcomes (e.g., needs, distress, goal concordance) may have been related to intervention components and their effect on process barriers in our conceptual model. 42,43

Sample Size and Power

Calculations were conducted via the mixed models with the differences in slopes option in PASS 2020 (Kayesville, UT). With a total of 130 participants at 8 days (n=65 per treatment arm), we will have 80% power to detect a differential NEST improvement between treatment groups of 8.80 units at 8 days (SD=21.1, ρ =0.64 between baseline and 8 days based on pilot data and an additional ongoing trial [NCT03506438]). To account for 10% dropout by 8 days, we plan to consent and randomize 150 participants (n=75 per treatment arm). This sample size will also provide a power of 80% (Type-I error of 5%, dropout rates as noted above) to detect a 2.33-unit PHQ-9 change (SD=5.3, ρ =0.6) at 8 days—far smaller even that it's 5.0-unit MCID. These estimates are based on our pilot work as well as an ongoing RCT (NCT03506438) we are conducting that uses the NEST

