This randomized clinical trial will compare PCplanner to a usual care control condition. The PCplanner intervention may reduce unmet needs and psychological distress, increase goal concordance, and reduce length of stay. Therefore, this intervention could hold great promise for helping many others in similar situations in the future. However, this is not certain. In fact, subjects in the usual care control condition may experience similar or even greater benefits to those described for PCplanner. Then again, they may receive no particular benefit. Nonetheless, study involvement puts subjects at low risk for any adverse physical or psychological risk. Therefore, the potential benefits for participation justify the minimal risk to those enrolled in the proposed study. Financial compensation will not be emphasized as a benefit of participation in research.

11. Adverse Events (AEs), Serious Adverse Events, (SAEs), Protocol Deviations (PDs) and Unanticipated Problems (UPs).

As noted above, this is considered a minimal risk study. Since the project intends to enroll critically ill patients who are elderly, and therefore, at risk of multiple and significant comorbidities, hospitalizations, and even death, adverse and serious adverse events will be limited to events that directly affect the overall well-being and safety of the family member (research subject). Additionally, given that this is a self-directed, survey based study, it is anticipated that compliance of research subjects (family member or clinician) will be less than 100% and/or completed within the protocol window. As such, events related to incomplete or missed study procedures will not be considered a protocol deviation and therefore will not be reported to the institutional or

Protocol Version: 5.1 Dated: 13 June 2022 Page 19 of 42

sponsor officials. Rather, events occurring outside of the study protocol will be documented and recorded by the study team in the web application, EDC, and/or study source documents as applicable.

All participants will have access to the principal investigator's contact information 24 hours a day (shown in the consent form). If a telephone interview is required, it will be conducted by a trained study team member who has been trained to be sensitive to the nature of these issues.

Adverse Events (AEs) and Serious Adverse Events (SAEs)

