Adverse events (AEs) generally would include extremely high distress levels (PHQ-9 score >25, GAD-7 score >20, PTSS score >34) or active suicidal ideation (i.e., endorsement of PHQ-9 suicidal ideation item plus a positive response to a branching logic item signifying active planning that would follow inquiring about a plan). A serious adverse event (SAE) would be a suicide attempt, a hospitalization, or death.

It is anticipated, in this study, for AEs to be extremely uncommon as it is a behavioral study. However, it is possible that participants could exhibit signs of and/or experience suicidal ideations with intent or thoughts of intent to act on such ideations. No other event, outside of suicidal ideation with intent or thoughts of intent to act on ideations will be considered an AE for this trial.

Like, AEs, it is not anticipated that SAEs will occur. However, for this study, an SAE would include a suicide attempt, a hospitalization (of family member), or death (of family member). All serious adverse events will be reported within the standard timelines required to the IRB, study sponsor, and/or DSMB, as appropriate and when applicable.

Protocol Deviations (PDs) and Unanticipated Problems (UPs)

Protocol deviations are errors made by study staff or deviations from plan made by study clinicians such as failure to conduct a family meeting. Unanticipated problems could consist of issues such as failure of the study staff to respond in a timely manner to suicidal ideation reported by a participant.

Given the nature of this study, it is anticipated that most enrolled family members will not complete their study surveys within the assigned protocol window. Additionally, it is expected that surveys may be missed as these are self-reported outcomes. As such, these will not be considered protocol deviations. Should other protocol deviations or unanticipated problems occur, they will be discussed with the PI, documented, and reported to the IRB, study sponsor, and/or DSMB, as appropriate and when applicable.

Period and Frequency for Event Assessment and Follow-Up

Protocol deviations and other unanticipated problems, as well as AEs and SAEs, will be recorded in the data collection system throughout the study.

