Appendix 4: Survey timelines and rules

T3 allowable window [contingent on T2 completion]; possible from study day 7 to study day 12
T3 will be available at 17:00 3 calendar days from time of T2 completion until 23:59 8 calendar days from time of T2 completion

Dated: 13 June 2022 Protocol Version: 5.1 Page 39 of 42

[figure not shown]

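### The T3 rules refuse late scores and any score without T2, although the protocol expects most caregivers to miss survey windows and allows for only 10% loss by day 8

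*Combined protocol and SAP*

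**What the plan says.** - **Primary outcome (Section 3, Primary Outcomes).** NEST at T3, 8 days after randomization.
- **Expected timeliness (Section 11, Protocol Deviations and Unanticipated Problems).** "it is anticipated that most enrolled family members will not complete their study surveys within the assigned protocol window". The next sentence adds a separate expectation: "Additionally, it is expected that surveys may be missed as these are self-reported outcomes". Neither is treated as a protocol deviation.
- **Acceptance rule (Section 5, Study data collection).** "Appendix 4 shows the timeline and acceptable time frames within which survey responses are allowed". T3 is set at day 8 with up to 4 further days. Appendix 3 gives the same margin, which ends on day 12.
- **T3 availability (Appendix 4).** T3 depends on T2 having been completed and is said to be possible from study day 7 to study day 12. The operating rule is: "T3 will be available at 17:00 3 calendar days from time of T2 completion until 23:59 8 calendar days from time of T2 completion".
- **Sample size (Section 8, Sample Size and Power).** 130 caregivers at 8 days give 80% power for a difference of 8.80 NEST units. "To account for 10% dropout by 8 days, we plan to consent and randomize 150 participants".
- **Analysis (Section 8, Aim 2).** An intention-to-treat mixed model of NEST over time. It has no stated rule for a late T3, and multiple imputation is named for T4 only.

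**The concern.** These statements pull against each other. If late completion is the norm and T3 shuts at a fixed time, some caregivers who would have answered a few days late are turned away. A caregiver who skips T2 is never offered T3, whatever their willingness. Both losses come from the survey rules and fall on the primary outcome, and Section 8's allowance covers dropout without mentioning either route.

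The closing day itself is not settled. One line of Appendix 4 gives a study day, and the other counts from T2. The two agree only for one T2 date. A site or programmer following one line would refuse scores that the other accepts.

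**Working it through.** **1. The plan's own figure (Section 8).** Inputs: SD 21.1, correlation 0.64, difference 8.80, 65 per arm, 80% power. The 5% type I error appears in the PHQ-9 sentence; two-sided is assumed because it reproduces the figure.

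- SD of change = 21.1 × √(2 × (1 − 0.64)) = 21.1 × √0.72 = 17.90.
- n per arm = 2 × (1.96 + 0.84)² × 17.90² / 8.80² = 65 after rounding up.
- Power with m per arm = Φ(8.80 / (17.90 × √(2/m)) − 1.96). At m = 65 this is 80.0%.
- PHQ-9 check: 5.3 × √(2 × (1 − 0.6)) = 4.74, which gives a detectable difference of 2.33, as stated.

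The stated design reproduces.

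**2. How much T3 loss it tolerates.** 130 / 0.90 = 144.4, so 145 would cover 10% loss, and 150 leaves a small surplus (150 × 0.90 = 135). The 130 needed are reached with loss up to 1 − 130/150 = 13.3%.

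**3. Power if more T3 scores are lost.** The documents give no T3 completion rate, so the rate is an assumption and is varied, with 150 randomized. The last column replaces the change-score SD by a baseline-adjusted one, 21.1 × √(1 − 0.64²) = 16.21.

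| T3 observed | Evaluable | Power at 8.80 | Detectable difference (80% power) | Power, baseline-adjusted |
|---|---|---|---|---|
| 90% | 135 | 81.5% | 8.63 | 88.4% |
| 86.7% (plan) | 130 | 80.0% | 8.80 | 87.2% |
| 80% | 120 | 76.8% | 9.16 | 84.4% |
| 70% | 105 | 71.2% | 9.79 | 79.4% |
| 60% | 90 | 64.5% | 10.57 | 73.1% |
| 50% | 75 | 56.7% | 11.58 | 65.2% |

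**4. The last T3 day.** T3 runs from T2 + 3 to T2 + 8 days.

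- T2 on day 4: 4 + 3 = 7 and 4 + 8 = 12, which matches the stated range of days 7 to 12.
- T2 on day 8, its last day under Appendix 3 (day 4, plus 4): 8 + 3 = 11 and 8 + 8 = 16.

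The stated range therefore fits only a T2 completed on day 4. Section 5's wording for T2 could be read as a limit of four days after randomization, which would remove the conflict, but Appendix 3 plainly adds four days to day 4.

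**5. The T2 condition.** With no T2 there is no date from which T3 can open, so a missed T2 also removes the primary outcome.

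**The case against.** **What a reader might infer.** The tempting reading is that T3 NEST would be missing for most of the sample and that power would be about 57%. The documents do not support it.

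- Section 11 speaks of study surveys together. A late T1, T2 or T4 could put a caregiver among the majority while T3 is on time.
- It treats late and missed as two separate things.
- It does not define the protocol window. If the nominal day is meant, a T3 up to four days late is still collected.
- Its purpose there is to exempt survey timing from deviation reporting. Earlier in Section 11 the same point is put more mildly: "it is anticipated that compliance of research subjects (family member or clinician) will be less than 100% and/or completed within the protocol window".

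**Other points on that side.** No text excludes a late response from analysis. The figure in Appendix 4 is not visible in the copy reviewed and may hold further rules. The 10% is labelled dropout, not late completion. Section 5 can be read as counting only T1–T3 completers toward the enrolment target, and it lets a caregiver who replies within a week of the last contact attempt resume. The mixed model also recovers some information from T1 and T2, so a completer change-score calculation overstates the power loss; the last column of the table shows roughly by how much.

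A reader might also suppose that lateness differs by arm, or that new DSMB reporting is needed. No passage gives timeliness by arm. Section 11 says out-of-protocol events are recorded, and Section 12 already has the DSMB review retention, completeness and timeliness.

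**What stands.** These points remove the claim about most of the sample. They do not reconcile the acceptance rule, the closing time, the T2 condition and the 10% allowance, or settle day 12 against day 16.

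**Conclusion.** The concern holds in limited form. As written, the survey rules refuse late T3 NEST scores and every T3 score from a caregiver who skipped T2, while the protocol itself expects poor adherence to windows. T3 loss could therefore exceed the 13.3% that the sample size tolerates. By how much is unknown.

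The power figures from 76.8% (80% observed) down to 56.7% (50% observed) are illustrations under assumed rates, using the plan's change-score SD of 17.90 and a two-sided 5% test; the 50% row is a worst case. With a baseline-adjusted SD, power is still 79.4% at 70% observed. The sample-size arithmetic is correct.

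The day 12 versus day 16 inconsistency rests on Appendix 3's T2 window. This should be amended, because primary-outcome scores that are turned away cannot be recovered later.

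**What to change.** 1. **Section 5 and Appendix 4.** Replace the T2-based opening and closing of T3 with one fixed outer study day counted from randomization. It should be the same in both arms and no earlier than day 16, the latest day the current rules already permit. State the origin of the count, since Section 3 calls baseline day 1 and Appendix 3 calls it day 0.
2. **Appendix 4.** Offer T3 whether or not T2 was completed. This concerns survey availability only and leaves the other uses of T2 alone.
3. **Section 8, Aim 2.** Include every T3 NEST received by the outer day in the intention-to-treat mixed model, with its actual day recorded. Use in-window responses only as a sensitivity analysis.
4. **Section 11.** Define the protocol window, and reconcile the expectation that most caregivers will miss it with the 10% allowance in Section 8.

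The cost is amendment wording and a change to the app's availability settings. The downside is that some T3 scores will fall several days after day 8; the recorded day and the sensitivity analysis show whether that matters. The change does not deal with T3 scores that never arrive.

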Analyses similar to those conducted for the NEST (primary outcome analyses) above will be performed for the secondary family caregiver hypotheses involving PHQ-9, GAD-7, and PTSS scores at T3 and T4. While family caregivers will be interviewed at T4 regardless of patient survival, patient death could complicate the analyses in two key ways: (1) Presence of missing data due to family loss to follow up (i.e., non-random missing data) and (2) differences in family caregiver distress by patient survival status (i.e., heterogeneous effect). 35 To address the impact of patient death on outcomes, after first exploring reasons for and predictors of dropout, we will conduct a 2-step supplemental analysis. In Step 1, missing T4 data due to loss to follow up among family caregivers of survivors will be multiply imputed via SAS PROC MI. In Step 2, we will account for T4 outcomes that are missing due to death via composite endpoint and principal stratification methods to estimate the causal effects of the intervention in the presence of these unidentified outcomes and complicated missing data patterns. 36,37 For the key patient outcome, receipt of goal concordant care, we will use logistic regression models adjusting for the stratification variables, to examine if rates at T3 differ by treatment group. The key healthcare systems outcome, post-randomization hospital length of stay (LOS), provides a unique challenge due to the high expected mortality rate (40-50%). In addition to descriptive analyses, steps to examine treatment group LOS differences will include: (1) a proportional hazards model with death treated as a censoring event; (2) a chi-square test of mortality rate differences; and (3) a Brunner-Manzel rank test for the composite death-LOS outcome. This last step implements a recently developed methodology of a composite outcome that incorporates a numerical value for death (i.e., coded as the worst possible outcome or the longest possible stay) in the observed LOS distribution. 38,39

Aim 3

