As noted above, the DSMB will have the power to stop the trial at their discretion. The following is a possible stopping plan that could be adapted by the study DSMB for inclusion in the final DSMB Charter. Because this is an early phase trial, we will not have formal stopping rules based on efficacy or futility. Criteria for intervention discontinuation and stopping based on safety concerns will be determined in partnership with the study DSMB and codified in the DSMB charter before enrollment begins. We propose a strategy similar to that included in our past ICU-based RCTs that included family caregivers (e.g., R01 HL109823, PI: Cox). Three-month all-cause mortality will be the primary adverse event for the patients in study. We will examine the distribution of deaths by treatment arm three times during the trial: at 15, 25, and 50 deaths. At each of these interim looks, we will examine the distribution of deaths by study group and conducted either a non-parametric sign test or Wilcoxon signed-rank test to test the difference in median number of deaths between the arms. We will use Haybittle-Peto guidelines and stringently set the p-value at 0.001 to flag a significant difference between arms at each of these interim looks. If this difference is observed, this would then indicate a closer examination of related constructs, as well as proximate causes and circumstances surrounding death (e.g., timing and location of death, withdrawal of life support or not, comorbidities and illness severity, clinician expectations of survival). We will use the Patient-Centeredness of Care Scale to provide additional information on the alignment of patient treatment and values at the time of death. Although past end of life interventions have not increased mortality, it is possible that by better focusing decision makers' attention on patients' values, higher mortality could be observed in the intervention group by identifying patients for whom prolonged life support would be a state worse than death (Patrick DL, et al. Ann Int Med. 139:410-415, 2003; Holloway RG, et al. JAMA. 298:802-804, 2007). Yet if PCplanner—a non-directive intervention—led to more decisions to forego life support, this would be ethically permissible if the treatments received reflected patient-centered care as assessed by the PCCS (Institute of Medicine, 2001; Lin GA, et al. Arch Intern Med. 169:1551-1553, 2009; Holloway RG, et al. 2007). The primary adverse event for family caregivers will be symptoms of psychological distress as measured by the PHQ-9 and PTSS at T2 and T3. We propose to examine the distribution of scores by treatment arm three times during the trial: at 25, 75, and 100 caregivers. Using methods similar to those above, we could examine circumstances more closely as per DSMB guidelines.

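### The proposed patient-death flag uses p=0.001 and a sign or signed-rank test although crossing it only prompts closer review, so by that rule even 60% v 30% mortality would be flagged in only about one trial in five

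*Combined protocol and SAP*

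**What the plan says.** Section 12 (Data Safety Monitoring Board, the paragraph on a possible stopping plan) makes three-month all-cause mortality the primary adverse event for patients. On timing: "We will examine the distribution of deaths by treatment arm three times during the trial: at 15, 25, and 50 deaths". On the test: "conducted either a non-parametric sign test or Wilcoxon signed-rank test to test the difference in median number of deaths between the arms". On the limit: "We will use Haybittle-Peto guidelines and stringently set the p-value at 0.001 to flag a significant difference between arms at each of these interim looks". On the consequence: "If this difference is observed, this would then indicate a closer examination of related constructs", together with the causes and circumstances of death.

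The paragraph offers this as a plan the DSMB could adapt for its charter, and it excludes formal efficacy and futility stopping. It gives no detection probability, harm margin, false-flag rate or sidedness. It does say that higher mortality in the intervention arm is possible, and that this could be ethically acceptable if care reflected patients' values.

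**The concern.** A limit as strict as 0.001 suits a decision that is costly to get wrong, such as stopping a trial. Here crossing it only starts a review. A missed excess of deaths is then the more serious error, and a needless review is the cheaper one. The closer examination is also the step the plan relies on to tell value-concordant deaths from harm. If the flag hardly ever fires, that step is seldom triggered by rule, and a DSMB told that no flag was raised may take more comfort than it should.

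The choice of test adds to the loss. Sign and signed-rank tests are for paired data. Deaths in two independent arms are not paired, and each arm has one count of deaths, so a difference in median number of deaths has no clear meaning. The only workable reading is a binomial test on how the deaths split, and that discards the number of patients at risk in each arm.

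**Working it through.** The plan states no detection probability for this flag, so there is no figure of its own to reproduce.

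**Inputs from the documents.** Looks at 15, 25 and 50 deaths, and p=0.001 at each (Section 12). 150 randomized, 75 per arm (Section 8, Sample Size and Power). Expected mortality 40-50% (Section 8, Aim 2, length-of-stay analysis), which gives 150 × 0.40 = 60 to 150 × 0.50 = 75 deaths, so all three looks would normally be reached. About 36 months of enrollment (Section 9).

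**Assumptions.** Harm scenarios of 50% v 40%, 55% v 35% and 60% v 30% (intervention v control), each averaging 45%. The test is two-sided; a one-sided 0.001 gives the same cut-offs.

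**Step 1: cut-offs.** Under equal mortality the number of intervention-arm deaths X among n is binomial(n, 0.5), with p = 2 × P(X ≥ c).

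| Deaths | Smallest flagged split | p | p with one death fewer |
|---|---|---|---|
| 15 | 14:1 | 0.00098 | 0.0074 |
| 25 | 21:4 | 0.00091 | 0.0041 |
| 50 | 37:13 | 0.00094 | 0.0026 |

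A 33:17 split at 50 deaths gives p = 0.033 and raises no flag.

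**Step 2: detection with the sign test.** With 1:1 allocation the intervention arm's share of deaths is s = pI/(pI + pC): 0.50/0.90 = 0.556, 0.55/0.90 = 0.611 and 0.60/0.90 = 0.667. The chance of any harm flag is P(X15 ≥ 14) + P(X15 < 14, X25 ≥ 21) + P(X15 < 14, X25 < 21, X50 ≥ 37), computed exactly.

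| Mortality | After look 1 | After look 2 | After look 3 |
|---|---|---|---|
| 50% v 40% | 0.2% | 0.4% | 0.9% |
| 55% v 35% | 0.7% | 1.6% | 4.9% |
| 60% v 30% | 1.9% | 5.4% | 18.8% |

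Simulating 75 patients per arm rather than fixing s gives about 15% at 60% v 30%.

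**Step 3: size against the trial.** By the Schoenfeld formula, 50 deaths give 20% power for a hazard ratio of 2 at alpha 0.001. Power of 80% would need 143 deaths, against the 60 to 75 expected.

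**Step 4: Fisher's exact test on deaths over patients randomized per arm.** Simulated with 75 per arm and uniform accrual over 36 months (assumed). The last column is the chance of a flag in either direction with mortality of 45% in both arms.

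| Threshold per look | 50% v 40% | 55% v 35% | 60% v 30% | Equal mortality |
|---|---|---|---|---|
| 0.001 | 1% | 10% | 41% | 0.2% |
| 0.01 | 7% | 31% | 71% | 2% |
| 0.05 | 20% | 56% | 88% | 8-9% |

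At 0.05 the false-flag rate in the harm direction alone is about 4%. At 0.001, Fisher's test flags 80% v 40% in about 58% of trials. The figures are rounded and carry simulation error of about one percentage point.

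**The case against.** The strongest reply is that the statistical flag is one safeguard among several. Every death is to be reported to the sponsor's program officer, the DSMB chair and the IRB within 72 hours with a short clinical summary (Section 11, Reporting Procedures). The DSMB is to scrutinize deaths and their causes, may ask for formal tests, may act on a clinically significant as well as a statistically significant rise in mortality, and may stop the trial at its discretion (Section 12). A reader might infer from the low detection figures that excess deaths would go unseen. The documents do not support that: unflagged here means unflagged by this rule. The rule is also only a proposal, and the charter that would fix it is not in the documents.

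A second reply is that the threshold does some work. It limits false alarms over repeated looks: the sign-test rule flags about 0.25% of trials with equal mortality, in either direction. Mortality is also compared again at the end by a chi-square test. So it would be too strong to say that 0.001 protects nothing.

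Third, a reader might infer that the 14:1, 21:4 and 37:13 splits apply to any two-sample test. They belong to the sign test. With equal denominators, Fisher's test at 0.001 needs about 13:2 at 15 deaths (16-20 patients per arm), 19:6 to 20:5 at 25 (26-35 per arm) and 34:16 to 35:15 at 50 (50-75 per arm). If 40-50% is read as control-arm mortality and doubled, Fisher's test at 0.001 fires in about 58-62% of trials at 80% v 40% and about 91% at 100% v 50%. Part of the loss is therefore due to the test and not the threshold.

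What remains is that this is the only numeric mortality criterion in the documents, and with the test the plan names it seldom fires.

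**Conclusion.** The point holds for the rule as the plan describes it. With the sign test at 0.001, mortality of 60% v 30% would pass all three looks unflagged about four times in five, and smaller excesses almost always. Both the threshold and the test contribute: at 60% v 30%, changing only the test raises detection from about 19% to 41%, and then relaxing the threshold to 0.05 raises it to about 88%.

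This rests on assumed harm scenarios, on uniform accrual for the Fisher figures, and on an expected mortality of 40-50% that the plan gives for the length-of-stay analysis and not for three-month mortality. The claim that a doubling usually goes unflagged holds for the sign test. It holds for Fisher's test at 0.001 only if 40-50% is overall mortality. DSMB discretion and the proposal status of the rule make the point less serious but do not remove it. It should be changed.

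**What to change.** In the stopping-plan paragraph of Section 12 and in the DSMB charter:

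- Replace the sign or signed-rank test with Fisher's exact test on deaths over patients randomized in each arm.
- Set the review flag at a review-level threshold, for example nominal two-sided 0.05 at each of the three looks.
- Report the mortality difference by masked arm with its 95% confidence interval at each look.
- State the flag's detection probability under named scenarios, and its false-flag rate.
- Keep any recommendation to stop separate from the flag and at DSMB discretion.

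The change takes a few sentences. Its price is about an 8-9% chance of one unnecessary DSMB review when mortality is equal. Both directions count because the test is two-sided and DSMB reports do not name the arm; about 4% falls in the harm direction. If that is thought too high, 0.01 cuts it to about 2%, with detection of about 7%, 31% and 71% in the three scenarios. The choice between the two is a judgement for the DSMB; the main need is a threshold chosen for review, with its error rates written down.
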